# 4.2.2 Trial design flowchart

# 4.2.3 Trial procedures

# 4.2.3.1 Trial procedures in a table form

#### Table 1. Visit schedule

Trial period	Screening/Randomization/Therapy initiation	Treatment		Further follow-up 	Unscheduled visits
Visits	Visit 1	Visit 2  Visit 3 		Visit 4	
Day after initiation of therapy	Day 1	Day 4 Day 5		Day 6/7	
Trial procedures					
Signing of the Informed Consent Form	•				
Demographic data (date of birth, sex, age)	•				
Measurement of weight and height	•				
Medical history	•				
Collection of complaints, actualization of anamnesis	•	•	•		•
Records on the concomitant therapy	•	•	•		•
Evaluation of the throat pain intensity according to VAS by a patient	•	•	•		
Fill-in of TSS questionnaire 	•	•	•		•
Physical examination (including topical examination)	•	•	•		•
Measurement of vital signs 	•	• *	•		•
Hematology 	•	• *	•		
Biochemistry 	•	• *	•		
Urine pregnancy test 	•				
12-lead ECG	•	• *	•		
Evaluation of inclusion/non-inclusion criteria	•				

<sup>1 A follow up visit will be held in the form of a phone contact with the patient to reveal the possible AEs.

<sup>2 In case of premature discontinuation, the follow-up procedures are the same as those at Visit 2.

<sup>3 Only for the Group B patients who did not meet the recovery criteria (total  $TSS \le 2$ ) at Visit 2 (Day 4) and continued the therapy.

<sup>4 Fill-in of TSS questionnaire by the Investigator (scores for every question should be summarized to obtain a total TSS score).

<sup>5 Systolic blood pressure (mm Hg), diastolic blood pressure (mm Hg), breathing rate (per minute), pulse rate (beats per minute), axillary body temperature (°C).

<sup>6 Hb, RBC, WBC with differential, ESR—at the trial site laboratory.

<sup>7 Total protein, AST, ALT, total bilirubin.

<sup>8 For women with the preserved childbearing potential only.

Trial period	Screening/rand omization/ther apy initiation	Treatment		Further follow-up 	Unscheduled visits
Visits	Visit 1	Visit 2 	Visit 3 	Visit 4	
Day after initiation of therapy	Day 1	Day 4	Day 5	Day 6/7	
Trial procedures					
Randomization	•				
Dispensing of the study drugs	•				
Dispensing of the patient's diaries	•				

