Return of the unused study drugs		• *	•		
Return of the patient's diaries		• *	•		
Evaluation of adverse events (including based on results of the throat and pharynx examination during the trial site visits)	•	•	•	•	•
Evaluation of exclusion criteria		•	•		•
Global evaluation of therapy tolerability by the patient and the physician		• *	•		•
Compliance evaluation (diary completion, administration of the study drugs)		•	•		•

Notes:

\* Only for Group A patients and those Group B patients who achieved the recovery criteria (total TSS score  $\leq 2$ ).

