## 3.8.2 Efficacy evaluation visit (Visit 2, Day 4 since the therapy initiation)

Visit 2 is conducted on Day 4; the patient must visit the trial site in the fasted state and bring the filled-in diary and unused drug. If Group B patients (ANTI-ANGIN® FORMULA) did not meet recovery criteria (total TSS  $\leq$  2) at Visit 2 (Day 4), they will require continuation of the therapy, and some procedures for those patients will be transferred for the next day (Visit 3, Day 5), see below. The patients will keep their diaries and the unused drugs.

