# 3.8.3 Trial completion visit for Group B patients (Visit 3, Day 5)

This visit is for Group B patients only (ANTI-ANGIN® FORMULA) who did not achieve the recovery criteria (total TSS  $\leq$  2) at Visit 2 (Day 4).

Visit 3 is conducted on Day 5; the patient must visit the trial site in the fasted state and bring the filled-in diary and unused drug.

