## 4.1.3 Secondary endpoints

The following statistical analysis methods are stipulated for the secondary efficacy endpoints:

- The frequency of  $\geq$ 50% total score reduction by the TSS questionnaire completed by the Investigator relative to baseline in both Angal and ANTI-ANGIN® FORMULA arms at Visit 2 (Day 4)—the response frequencies will be compared in each time point using the Fisher's exact test.
- Total score reduction by the TSS questionnaire, as well as reduction in symptoms (sore throat, difficulty in swallowing, salivation, erythema and fever) after 3-day therapy, at Visit 2 (Day 4), relative to baseline total score—the between-arm comparison will be carried out using the Mann–Whitney test due to non-symmetrical nature of the scores distribution in the TSS scale.
- A period of time required for the symptoms resolution defined by the patient's diary (subjective patient's evaluation), but not more than 5 days within the trial (for patients who achieved the relevant outcome)—the between-arm comparison will be carried out using t-test or the Mann–Whitney test depending on the distribution character. The survival will not be evaluated due to low duration of the trial.
- The proportion (%) of patients who fully recovered on Day 4 in Group A and on Day 5 in Group B (disease outcome according to the objective evaluation by the Investigator, the total score by the TSS questionnaire  $\leq 2$ )—the between-arm comparison will be carried out using the Fisher's exact test.
- A change in the sore throat intensity by 100 mm VAS (visual analogue scale filled in by the patient) at the beginning, after 3 days of therapy, and at the end of treatment in both groups—the between-arm comparison will be carried out using the t-test.

A secondary endpoint analysis will be conducted both for the ITT (main analysis) and PP populations (additional analysis).

A multifactorial analysis of the secondary endpoints is not envisaged.

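### Three secondary between-arm tests use unequal follow-up; the achievers-only time-to-relief test is the one that most needs changing

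*SAP*

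**What the plan says.** SAP 4.1.3 and Protocol 9.1.3 prescribe between-arm tests for five secondary efficacy endpoints, in the ITT and PP sets. Three of them depend on when follow-up ends.

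- **Full recovery (TSS ≤ 2), Fisher's exact test:** "The proportion (%) of patients who fully recovered on Day 4 in Group A and on Day 5 in Group B".
- **Time to symptom relief from the diary, t-test or Mann–Whitney:** capped at 5 days and restricted to patients who achieved relief. The SAP adds: "The survival will not be evaluated due to low duration of the trial".
- **VAS change, t-test:** "at the beginning, after 3 days of therapy, and at the end of treatment in both groups".

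The visit schedule sets the end of follow-up. In Protocol Table 1, Visit 3 (Day 5) is "Only for the Group B patients who did not meet the recovery criteria" at Visit 2, and SAP 3.8.3 agrees: "This visit is for Group B patients only". Diary and drug return at Visit 2 carry the footnote "Only for Group A patients and those Group B patients who achieved the recovery criteria". For Group B patients not recovered at Visit 2, SAP 3.8.2 says: "The patients will keep their diaries and the unused drugs".

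Several same-day comparisons at Visit 2 are also planned: the primary endpoint, the frequency of at least 50% TSS reduction ("the response frequencies will be compared in each time point using the Fisher's exact test"), the change in TSS, and VAS after 3 days. TSS ≤ 2 at Visit 2 appears only as counts by arm in SAP Table 19, with no p row.

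**The concern.** A Group A patient who is not well at Visit 2 has no later scheduled assessment and hands in the diary. An identical Group B patient is seen again on Day 5 and goes on recording. The arms are then compared on results gathered over different lengths of time.

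The effect is not in one direction. For recovery and end-of-treatment VAS, the extra day can only add improvement to Group B, so these lean towards the comparator. For time to relief, the extra day adds late relief times to Group B's average, while the matching Group A patients are left out of the analysis, so Angal looks faster. Two identical drugs could produce nominally significant results pointing opposite ways. What is at stake is a secondary p-value reported as a drug difference when it reflects the schedule.

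**Working it through.** The plan gives no power or expected rate for these endpoints, so there is no figure of its own to reproduce. The arm size of 128 is from Protocol 9.2. All recovery, relief and VAS inputs below are assumptions, because the documents give no TSS ≤ 2 rate, next-day rate, relief-time distribution or VAS standard deviation. Both drugs are taken to be identical, so any rejection above the nominal level comes from the schedule.

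**Recovery.** Let p be the share with TSS ≤ 2 on Day 4 and h the share of the rest who recover by Day 5. Group A's expected rate is p and Group B's is p + (1 − p)h, so the gap is (1 − p)h. With p = 0.65, the rejection rate of the two-sided Fisher test (p < 0.05), by exact enumeration, is:

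| h | Group B rate | Gap, points | Rejection |
|---|---|---|---|
| 0 (common day) | 65.0% | 0 | 3.7% |
| 0.10 | 68.5% | 3.5 | 7.2% |
| 0.20 | 72.0% | 7.0 | 18.9% |
| 0.30 | 75.5% | 10.5 | 39.9% |
| 0.40 | 79.0% | 14.0 | 65.8% |

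If the daily recovery rate is constant over the three days, h = 1 − (1 − p)^(1/3). For p = 0.50, 0.65 and 0.80 this gives h = 0.206, 0.295 and 0.415, gaps of 10.3, 10.3 and 8.3 points, and rejection in 33.9, 38.7 and 38.1% of trials.

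**Time to relief.** Visit 2 is on the morning of Day 4 (Protocol 7.2), so take Group A as observed to 3 days, and Group B to 3 days, or to 4 days if the diary is kept. For an exponential relief time with rate λ, the mean among those relieved by time c is 1/λ − c·e^(−λc)/(1 − e^(−λc)). If 65% are relieved by 3 days, λ = −ln(0.35)/3 = 0.350 and 1/λ = 2.858.

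- c = 3: 2.858 − 3 × 0.350/0.650 = 1.24 days.
- c = 4: 2.858 − 4 × 0.247/0.753 = 1.55 days.

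That is a difference of 0.31 days with no drug effect. It is an upper bound, because it assumes that every unrelieved Group B patient keeps the diary. In fact the diary is kept on the investigator's TSS, while relief is the patient's own judgement. Simulation with relief medians of 2 to 3 days gives:

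- All unrelieved Group B patients keep the diary: Mann–Whitney rejects in 36–42% of trials.
- 50–70% keep it, independently of later relief: about 13–25%.
- Keeping it depends on TSS recovery, correlated 0.5–0.8 with relief, with Day 4 recovery of 50–80%: Mann–Whitney 5.7–22.8%, t-test 6.3–36.8%. At 80% Day 4 recovery, a repeat run of 1,500 trials per cell gave Mann–Whitney rates of 5.9–8.7%.
- Log-rank on all patients, both arms cut at 3 days: 4.3–5.8%.

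**End-of-treatment VAS.** The bias is the unrecovered share times the extra one-day fall. With 35% unrecovered and falls of 5 and 10 mm, it is 0.35 × 5 = 1.75 mm and 0.35 × 10 = 3.5 mm. From the noncentral t distribution, rejection is 10.7% (SD 20 mm) or 8.6% (SD 25 mm) for the smaller fall, and 28.6% or 20.0% for the larger.

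**The case against.** The strongest reply is that the unequal days are a disclosed design choice. Protocol 3.2 defines the comparison as a course of up to 4 days against one of up to 5 days, and the recovery endpoint names both days wherever it appears, including SAP Figure 5. This stands. A reader might infer that the recovery test is a mistake or conceals its timing, but the documents do not support that: it is a legible end-of-course comparison that leans against the sponsor's own product. The reply does not rescue time to relief, where patients without relief drop out of both arms.

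A reader might also infer that no same-day evidence is planned, or that SAP Table 17 would yield a false p-value at Visit 3. Neither holds. Same-day tests of VAS and of two other TSS measures are planned, and Table 19 tabulates TSS ≤ 2 at Visit 2. The Visit 3 p cell is a feature of the generic table template: Group A has no Visit 3, so nothing can be computed there.

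Finally, the rejection rates rest on assumed inputs and the ranges are wide. That also stands. The direction of each lean is firmer than its size: it needs only that some unrecovered Group B patients improve, or record first relief, between the two visits.

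**Conclusion.** The point holds for all three tests, with unequal weight. Time to relief is the main defect and should be changed. Its bias favours Angal, with Mann–Whitney rejection in about 6–25% of trials of identical drugs when some unrelieved Group B patients keep the diary. It falls close to nominal when Day 4 recovery is high. Recovery and end-of-treatment VAS are minor. The first needs a same-day companion and a label, and the second already has its same-day test.

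It would be tempting to conclude that the non-inferiority finding is compromised. It is not. The primary endpoint is assessed on Day 4 in both arms, and SAP 4 rests the non-inferiority conclusion on it alone, treating secondary variables as of research interest. Nor do the three biases together favour one drug.

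**What to change.** 1. **Recovery.** Add a between-arm Fisher test of TSS ≤ 2, with the difference and its confidence interval. Use, in both arms, the row of the TSS form (Protocol Appendix 2) scored after 3 days of therapy and before the first Day 4 dose. Do not use the form's Visit 2/3 disease-outcome row for this test, since that would bring the asymmetry back. Keep the Day 4/Day 5 figure, label it as end of course with unequal days, and do not interpret it as a drug difference.
2. **Time to relief.** Replace the achievers-only test with Kaplan–Meier curves and a log-rank test in all ITT patients. Cut both arms at the last diary entry before Visit 2 and censor patients without relief at that point. Delete the SAP 4.1.3 sentence ruling out survival analysis, and its counterpart in Protocol 9.1.3. The sponsor should pre-specify the event (for example first or sustained YES to the diary question in Protocol Appendix 3) and the handling of withdrawals for worsening, identically in both arms.
3. **VAS.** Make the planned change after 3 days the between-arm test, and report end-of-treatment VAS descriptively.

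The endpoint lists, SAP 4.1.3, Tables 17 and 19 and Figures 4–6 should be aligned. The route is a protocol amendment (Protocol 11.2), or a justified deviation listed in the SAP before the final analysis (Protocol 9.6). On the second route, the statement in SAP 1 that no departures from the protocol are foreseen must also be edited.

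The cost is a little extra analysis, the approval that a change of statistical methods requires if made by amendment, and the loss of Group B's Day 5 diary data from the time-to-relief test. No new visits, patients or data are needed.

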## 2.2 Secondary endpoints

- The frequency of  $\geq$ 50% total score reduction according to the TSS questionnaire completed by the Investigator as compared to the baseline in both Angal and ANTI-ANGIN® FORMULA groups at Visit 2 (Day 4).
- Total score reduction according to the TSS questionnaire, as well as a reduction in the symptoms (sore throat, difficulty in swallowing, salivation, erythema, and fever) after a 3-day therapy, at Visit 2 (Day 4), as compared to the baseline total score.
- A period of time required for disappearance of the disease symptoms, determined according to the patient's diary (subjective patient's evaluation), but no more than 5 days during the trial—for patients who have achieved the corresponding outcome.
- A proportion (%) of patients who fully recovered by Day 4 in Group A and by Day 5 in Group B (the outcome of a disease according to the objective evaluation by the Investigator, the total score according to the TSS questionnaire  $\leq 2$ ).
- A change in the sore throat intensity by 100 mm VAS (visual analogue scale filled in by the patient) at the beginning, after 3 days of therapy, and at the end of treatment in both groups.

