## VAS (visual analogue scale) to evaluate pharyngalgia severity:

The patient will fill in this scale at every visit to the trial site (Visits 1, 2, 3, where applicable). Calibrated scales 100 mm in length with the relevant measuring instruments will be provided for the clinical trial.

The patients should evaluate their pain severity according to VAS at every visit (if possible, before administration of the painkillers (if those are required) or the study drug/comparator drug).

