# 3.8 Acceptable deadlines for visits and a scope of investigations

The data obtained at Visit 1 (Day 1) will be considered to be the initial data for the endpoint analysis.

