## 3.10 Significance level

All statistical analyses in this trial will be conducted at 95% significance level (a threshold p value for confirmation of statistical significance is below 0.05), except for the primary endpoint where a one-sided statistical criterion will be used with 95% significance level (a threshold p value is below 0.05). The two-sided statistical criteria will be used for all other parameters.

For the primary endpoint evaluation, 90% CI will be calculated for the proportions difference with further evaluation of its lower boundary limit.

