## 4 Analysis plan

For non-inferiority confirmation, a two-sided 90% CI will be calculated for the proportion difference of the primary efficacy parameters (no pain after 3 days of therapy on Day 4 according to TSS) with further evaluation of its lower boundary limit.

A non-inferiority conclusion will be made relating to the primary parameter only which will confirm the claimed efficacy. Secondary variables (including secondary efficacy and safety parameters) will be used for the research interest. Correction for multiple comparisons is not envisaged due to the trial arms number.

Descriptive statistics will include data for all randomized patients. Descriptive statistics parameters to be calculated for the quantitative variables are listed below:

- Quantity of observations (n);
- Arithmetic mean (M);
- Standard deviation (SD);
- 95% confidence interval for the mean (95% CI);
- Minimal value (min.);
- Maximal value (max.);
- Median (Me);
- Interquartile range (IQR).

For the variables presented as qualitative and serial parameters, the absolute (n) and relative (%) incidences will be calculated for every category, as well as 95% CI (unless otherwise specified).

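### VAS is compared between arms by an unadjusted t-test although baseline VAS is collected; pre-specify a Day 4 ANCOVA on Visit 1 VAS

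*SAP*

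**What the plan says.** SAP 2.2 lists as a secondary endpoint "A change in the sore throat intensity by 100 mm VAS", rated by the patient at the start, after three days and at the end of treatment. For the analysis, SAP 4.1.3 and protocol 9.1.3 state that "the between-arm comparison will be carried out using the t-test". SAP 4.1.3 ends its list of methods with "A multifactorial analysis of the secondary endpoints is not envisaged".

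The baseline value exists. Protocol Table 1, protocol 4.2.3.2.4 and the VAS paragraph under SAP 2.2 have the scale completed at Visit 1, Visit 2 and, where it applies, Visit 3. SAP 3.8 fixes the baseline: "The data obtained at Visit 1 (Day 1) will be considered to be the initial data for the endpoint analysis".

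On status, SAP 4 rests the non-inferiority conclusion on the primary parameter alone and says "Secondary variables (including secondary efficacy and safety parameters) will be used for the research interest". SAP 3.10 sets the level for these tests ("a threshold p value for confirmation of statistical significance is below 0.05") and the sidedness ("The two-sided statistical criteria will be used for all other parameters").

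The VAS shell, SAP Table 17, has columns for Visits 1, 2 and 3, summary statistics by arm and a p row. It has no change column and no between-arm difference.

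**The concern.** A strong predictor of the Day 4 score is recorded before treatment and then left out of the comparison. A t-test on change in effect fixes the baseline slope at 1. A t-test on Day 4 scores fixes it at 0. Unless the true slope happens to equal the fixed value, precision is lost and part of any chance baseline difference stays in the estimate. Protocol 9.1.1 compares the arms at baseline but does not say what follows for the VAS analysis if they differ.

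Two features make this worth a sentence. The objective is non-inferiority, yet for VAS the plan yields only a p value and arm-wise intervals. A non-significant t-test does not show that the arms are similar, whereas an adjusted difference with its interval would be informative. Naming the model would also settle which quantity is tested, because the endpoint is worded as a change while Table 17 shows only visit scores.

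**Working it through.** **Inputs from the documents.** The test is a t-test with no covariate (SAP 4.1.3). Baseline is Visit 1 (SAP 3.8). Allocation is 1:1, with 128 evaluable patients per arm, 256 in total (protocol 9.2). The plan gives no SD, correlation, target difference or power for VAS, so it has no figure of its own to reproduce.

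**Assumed inputs.** rho is the correlation between Visit 1 and Day 4 VAS, taken over 0 to 0.9. k = SD(Day 4)/SD(Visit 1), taken as 0.75, 1 and 1.25. Both are assumed to be the same in the two arms.

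**Variance of the between-arm contrast**, in units of the baseline variance and up to a common factor for sample size:

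- t-test on change: 1 + k² − 2·rho·k
- t-test on raw Day 4 scores: k²
- ANCOVA: k²(1 − rho²)

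**Direction of the gain.** Change minus ANCOVA: 1 + k² − 2·rho·k − k² + rho²k² = (1 − rho·k)², which is never negative. Raw minus ANCOVA: k²rho², also never negative. ANCOVA is therefore at least as precise whichever quantity the t-test is applied to, apart from one degree of freedom (about 1/256 = 0.4%).

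**Size against the change score.** With k = 1 the ratio is (1 − rho²)/(2(1 − rho)) = (1 + rho)/2, so the cut is (1 − rho)/2. Worked cells:

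| k | rho | Change | ANCOVA | Cut |
|---|---|---|---|---|
| 0.75 | 0.3 | 1.1125 | 0.5119 | 54.0% |
| 0.75 | 0.6 | 0.6625 | 0.3600 | 45.7% |
| 1 | 0 | 2.0 | 1.00 | 50% |
| 1 | 0.3 | 1.4 | 0.91 | 35% |
| 1 | 0.6 | 0.8 | 0.64 | 20% |
| 1 | 0.9 | 0.2 | 0.19 | 5% |
| 1.25 | 0.3 | 1.8125 | 1.4219 | 21.6% |
| 1.25 | 0.6 | 1.0625 | 1.0000 | 5.9% |
| 1.25 | 0.8 | 0.5625 | 0.5625 | 0% |

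The gain vanishes in the last row because rho·k = 1 there, so the change score already uses the right slope.

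**Size against raw Day 4 scores.** The cut is rho²: 9% at 0.3, 25% at 0.5, 36% at 0.6. It rises with rho, whereas with k = 1 the gain over the change score falls.

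**In terms of the standard error.** With k = 1, 1 − √0.80 = 10.6% at rho 0.6 and 1 − √0.65 = 19.4% at rho 0.3.

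**Baseline imbalance.** The true slope of Day 4 on Visit 1 is rho·k. Per 1 mm of chance imbalance, the change score leaves rho·k − 1 mm in the estimate and the raw score leaves rho·k mm; ANCOVA removes it on average. At k = 1 and rho 0.5 these are −0.5 mm and +0.5 mm.

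**The case against.** The strongest reply is that nothing here is an error. A two-sample t-test is valid and unbiased under randomisation. The SAP states openly that it will keep the secondary analyses simple and exploratory. VAS has no margin and no power, and no decision turns on it. All of that stands and limits the weight of the point. It does not reduce the point to taste, because the better analysis uses data already collected and, in large samples, is at least as precise under either reading of Table 17.

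A reader might go further than the documents allow in four ways.

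- *A definite gain of 20–35%.* That range needs equal SDs and rho between 0.3 and 0.6, neither of which is stated. Equal SDs are doubtful: entry requires a total TSS of at least 5, and 63–65% are expected to have no sore throat on Day 4, which suggests a floor. The direction of the SD ratio is unknown.
- *The change score over-corrects whenever the correlation is below 1.* This holds only for equal SDs. In general the condition is rho·k < 1. At k = 1.25 and rho 0.9 the slope is 1.125, and the change score under-corrects.
- *VAS is the only patient-rated pain measure.* The diary (protocol Appendix 3) has a yes/no throat-pain item for each lozenge, and time to symptom relief is also rated by the patient.
- *A sharper VAS result would guard against open-label bias.* The diary tells patients that they know their drug. Precision does not remove that bias.

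**Conclusion.** The point holds as a low-severity improvement: a collected baseline is left unused in a between-arm comparison that would gain from it. The direction of the gain needs no assumed value of rho or k, only large samples and a common covariance structure in the arms. Its size does need them. For rho 0.3 to 0.6, the variance cut against the change score is 46–54% at k = 0.75, 20–35% at k = 1 and 6–22% at k = 1.25. If the planned test is on raw Day 4 scores, it is 9–36%.

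It would be wrong to infer that the planned t-test is invalid or that the non-inferiority conclusion is at risk. The primary endpoint is binary and is analysed separately.

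**What to change.** In protocol 9.1.3 and SAP 4.1.3, state that Day 4 VAS will be analysed by ANCOVA with arm and Visit 1 VAS as terms, and that the adjusted between-arm difference will be reported with its 95% CI. Word an exception to the sentence against multifactorial analysis. Add an adjusted-difference row to SAP Table 17. The t-test may stay as a supportive result, with a statement of whether it is on change or on visit scores.

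The model is limited to Day 4, when both arms are measured on the same day. It does not repair the end-of-treatment comparison, where Group A is measured on Day 4 and Group B on Day 4 or Day 5. That comparison should be presented with this difference in timing stated.

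The cost is one degree of freedom and a small text change; no new data are needed. There is some procedure. Protocol 11.2 treats changes to statistical methods as significant amendments, although protocol 9.6 also lets a deviation be listed and justified in the SAP and final report. If that route is used, the statement in SAP 1 that the SAP departs nowhere from the protocol must be adjusted.
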